So, the relative increase in variance due to missing values is 32%, indicating that $1.32 * 180$ subjects = 238 subjects are required to attain the same power that would be attained in a sample of 180 subjects who all complete the study. In other words, 238 subjects must be enrolled in the study, with 180 completing, to achieve the same power when using multiple imputation as would be achieved if 180 subjects were enrolled and all completed. If multiple imputation were not used, and only complete cases were analyzed, approximately 238 subjects would have to be enrolled to produce 180 complete cases. Thus, multiple imputation is more efficient than complete-case analysis, in addition to avoiding bias due to MAR missingness.

A secondary analytic approach will be to use mixed models on non-imputed data. Mixed models can be used to analyze repeated measures data without discarding subjects with missing data. Mixed models will be used for measures only obtained at pre- and post-assessment and on measures with interval assessments. Analytic approaches for each set of specific aims and hypotheses are detailed below.

Specific Aim 1: To conduct an RCT of an early dyadic intervention for PO-MDD, PCIT-ED, compared to a WL control condition.

Hypothesis 1A: Compared to those randomized to the WL, preschoolers who are first randomized to PCIT-ED will show significantly increased rates of remission, greater reductions in MDD symptoms, and decreases in impairment.

Hypothesis 1B: Compared to those randomized to the WL, preschoolers who are first randomized to PCIT-ED will show significantly greater increases in emotional competence measured by the ability to accurately identify emotions in themselves and others and the ability to effectively regulate intense emotions.

Hypothesis 1C: Compared to those on the WL, parents who are first randomized to PCIT-ED will show significantly greater increases in emotion skill learning (ESL) and reductions in MDD symptoms and parenting stress.

Analytic Approach: Continuous post-assessment scores will be compared between PCIT-ED and WL groups using analysis of covariance, covarying for pre-assessment scores. The stratification variables, gender and externalizing comorbid diagnoses, will also be included as covariates in the models.

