To assess parental ESL as a potential mediator of the relationship between treatment group and child treatment response, a macro (for SAS or SPSS) developed by Hayes will be utilized. For mediation analyses, the PROCESS macro estimates path coefficients in a mediation model and generates bootstrap confidence intervals for the indirect effects of the independent variable on the dependent variable through a mediator variable. It is also possible to include covariates not proposed to be mediators in the model. Paternal ESL will be evaluated by entering post ESL score into the model as a potential mediator, with treatment group as the independent variable and change in PAPA MDD severity sum score as the dependent variable.

Power for Mediation: To estimate power for this mediation analysis, the following steps were taken. First, we expect the difference in MDD severity sum change score in the two groups to be approximately 2.5, with a SD of 4.69 (based on our pilot study). With 90 subjects per group, an alpha of 0.05, and a 1-sided test, power=0.97. Next, we expect the correlation of change in MDD severity sum score and ESL score to be approximately 0.25. Using Fisher's Z transformation with a sample size of 180, the correlation of 0.25 transforms to $Z = \tanh(0.25) * \sqrt{180-3} = 3.398$. Subtracting 1.96 gives 1.438, corresponding to power=0.92. Thus, we will be well-powered to detect a mediation effect.

To assess parental emotional intelligence (EI) as a potential moderator of treatment response, the PROCESS macro will be used. For moderation analyses, the PROCESS macro

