estimates a moderation model with the effect of the independent variable on the dependent variable moderated by a proposed moderator variable. The independent variable (ESL score) and proposed moderator variable (pre-assessment parental EI) are centered to eliminate any multicollinearity effects. The macro generates the conditional effects of ESL score on the dependent variable (MDD severity sum score) at values of EI score equal to selected percentiles (e.g., 10th, 25th, 50th, 75th, and 90th percentiles) of the distribution in the sample. The Johnson-Neyman technique will be used to identify the values of EI score at which point the effect of ESL score changes from statistically significant to statistically non-significant. If EI score is found to be a significant moderator, the independent and moderator variables (ESL score and pre-assessment EI score) will be dichotomized so that all subjects fall into 1 of 4 categories (low ESL with low parental EI, low ESL with high parental EI, high ESL with low parental EI, and high ESL with high parental EI). Post-hoc pair-wise comparisons of treatment outcome in these 4 groups will be conducted.

Power for Moderation: To estimate power for this moderation analysis, a simulated dataset of 90 PCIT-ED subjects was created. This dataset contained variables for parental ESL, parental EI, and change in MDD severity sum score. Random data was generated for 45 “high EI” subjects and 45 “low EI” subjects assuming normally distributed data for each of these variables, with SD’s based on our pilot study (SD=0.22 for ESL, SD=15.6 for EI, SD=4.69 for MDD change score). The mean scores for the random normally distributed data varied in the two groups as we expect it to in the proposed study. For the “high EI” group, assumed means were 2.1 for ESL, 118 for EI, and -6.5 for MDD change. For the “low EI” group, assumed means were 2.5 for ESL, 99 for EI, and -1 for MDD change. Running the PROCESS macro on the simulated dataset yielded a significant interaction of ESL and EI, with a coefficient=0.2440 and SE=0.0758. Subtracting 1.96 from the corresponding t score (3.219) gave Z=1.259, which corresponds to power=0.90.

Specific Aim 3: To investigate whether reductions in depressive symptom severity and diagnostic remission is sustained 18 weeks after treatment has ended in those randomized to PCIT-ED first.

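### The ESL by EI moderation model has an inconsistently stated outcome and no baseline severity term

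*Combined protocol and SAP*

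**What the plan says.** All places below are in the PCIT-ED Statistical Analysis Plan.

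- **Specific Aim 2, Analytic Approach, moderation.** The purpose is given as "To assess parental emotional intelligence (EI) as a potential moderator of treatment response". The macro is then said to produce the "conditional effects of ESL score on the dependent variable (MDD severity sum score"), at chosen EI percentiles, followed by a Johnson-Neyman analysis. No assessment time is attached to the outcome, and no baseline severity term is listed.
- **Specific Aim 2, Power for Moderation.** The simulated data are for 90 PCIT-ED subjects: "This dataset contained variables for parental ESL, parental EI, and change in MDD severity sum score". The SD used for that change score is 4.69, and the stated power is 0.90.
- **Specific Aim 2, Analytic Approach, mediation.** The parallel model has "change in PAPA MDD severity sum score as the dependent variable". The same text remarks that "It is also possible to include covariates not proposed to be mediators in the model", but names none.
- **Specific Aim 1, Analytic Approach.** Continuous outcomes are compared "using analysis of covariance, covarying for pre-assessment scores", with the stratification variables also in the model. This statement sits under Aim 1 and is not carried over to Aim 2.

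**The concern.** The analysis text and the power text for the same model name different variables, and nothing elsewhere in the plan says which governs. Until that is settled, the outcome could be chosen after the data are seen.

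The choice matters because randomisation does not protect this model. ESL is a skill that parents acquire to differing degrees, EI is a parental trait, and the power dataset lies wholly within the PCIT-ED arm. Children's starting severity may differ across levels of either. If the outcome is the raw post score, a child who falls from 12 to 6 ranks worse than one who stays at 5, which is not treatment response. If it is the change score, children who start higher have more room to fall, and regression to the mean works in the same direction. Either way, starting severity can enter the conditional ESL effects and move the EI values at which Johnson-Neyman declares them significant. Leaving out a predictor that the trial already collects also gives up precision.

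**Working it through.** **1. The plan's own figure.** From Power for Moderation: coefficient 0.2440, SE 0.0758, critical value 1.96.

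- t = 0.2440 / 0.0758 = 3.219
- 3.219 − 1.96 = 1.259
- Power = Φ(1.259) = 0.896, stated as 0.90

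The final arithmetic reproduces. The figure belongs to the change score without baseline adjustment. This step does not test how the coefficient and SE arose.

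**2. Residual variance under three outcomes.** Let r be the pre-post correlation of MDD severity and s the common pre and post SD. The documents do not give r, so 0.3, 0.5 and 0.7 are assumptions. Equal variances are also assumed, and ESL, EI and their product are ignored as predictors.

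- Raw post score: s²
- Change score: 2(1 − r)s²
- Post score adjusted for baseline: (1 − r²)s²
- Adjusted relative to raw: 1 − r²
- Adjusted relative to change: (1 − r²) / [2(1 − r)] = (1 + r)/2

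Holding the change SD at the plan's 4.69 gives s = 4.69/√(2(1 − r)).

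| r | Raw SD | Change SD | Adjusted SD | Variance cut vs raw (r²) | Variance cut vs change ((1 − r)/2) |
|---|---|---|---|---|---|
| 0.3 | 3.96 | 4.69 | 3.78 | 9% | 35% |
| 0.5 | 4.69 | 4.69 | 4.06 | 25% | 25% |
| 0.7 | 6.05 | 4.69 | 4.32 | 49% | 15% |

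The cut against raw does not need equal variances. The cut against change does. With k the ratio of pre SD to post SD, the adjusted-to-change ratio is (1 − r²)/(1 + k² − 2rk). This never exceeds 1, because the denominator minus the numerator is (k − r)². The gain is zero when k = r.

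**3. Confounding of the ESL effect.** Suppose baseline severity correlates c with ESL, and ESL has no relation to post severity once baseline is fixed.

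- Raw post score: correlation with ESL = rc
- Change score: correlation with ESL = −c√((1 − r)/2)

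With c = −0.2 (assumed) and r = 0.3, 0.5, 0.7, these are −0.06, −0.10, −0.14 for raw and +0.12, +0.10, +0.08 for change. The two outcomes err in opposite directions, and neither is free of baseline. These are correlations with ESL itself. They bear on the conditional ESL effects, not on the interaction coefficient.

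**4. Confounding of the interaction.** Simulation with n = 90, no true effect on response given baseline, and a two-sided 5% test of the ESL by EI term (3,000 runs per setting):

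| Baseline's correlation with the ESL × EI product | r | Raw post | Change | Adjusted |
|---|---|---|---|---|
| 0 | 0.3 / 0.5 / 0.7 | 5.3 / 5.1 / 4.5% | 5.2 / 5.2 / 4.9% | 5.5 / 5.3 / 4.9% |
| 0.3 (assumed) | 0.3 / 0.5 / 0.7 | 13.5 / 26.6 / 47.4% | 37.2 / 28.1 / 18.3% | 4.7 / 5.5 / 5.2% |

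With baseline correlated −0.3 with both ESL and EI but not with their product (5,000 runs per setting), the raw-score interaction test rejected in 4.8%, 4.8% and 5.5% of runs. A linear link goes into the main effects, which the model already contains.

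**The case against.** The strongest defence is that the outcome is simply the change score. The parenthetical sits in a sentence about macro output, the mediation model just before it uses change, and the power simulation ran the same macro on change. That reading is at least as likely as the raw score. A reader might infer that the plan has committed itself to the raw post score, but the documents do not support this. They support only that the outcome is not clearly defined. The defence does not dispose of the point, because the change score without a baseline term is itself open to baseline confounding (steps 3 and 4).

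A reader might also infer that any link between baseline severity and ESL or EI would be mistaken for moderation. It would not: step 4 shows that a link with the product is needed, and the documents give no evidence of one.

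Finally, a reader might infer that the analysis has less power than the stated 0.90. That figure was computed for the change score. The variance of the raw post score relative to change is 1/[2(1 − r)], or 0.71, 1.00 and 1.67 at r = 0.3, 0.5 and 0.7. The raw score is therefore less precise than the sized variable only if r exceeds 0.5, and r is not given.

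The equal-variance assumption can also be challenged: only children who still meet MDD criteria at baseline are randomised, which may narrow the baseline spread. That could shrink the gain against the change score, but it cannot turn the gain into a loss of residual variance.

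**Conclusion.** The point holds as an inconsistency of definition plus a missing covariate. The moderation outcome is stated one way for analysis and another for sizing, and under neither reading is baseline severity in the model.

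Under equal variances and r of 0.3 to 0.7, the precision forgone is 9% to 49% of residual variance if the raw post score is meant, and 35% down to 15% if change is meant. The possible confounding of the conditional ESL effects and the Johnson-Neyman region is real in principle. Its size depends on correlations that the documents do not supply. Bias in the interaction is a narrower possibility, limited to a relation between baseline severity and the ESL by EI product. Adjustment removes the part of this confounding that a linear term in measured baseline severity can capture.

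This is a secondary aim and the primary comparison is unaffected, but the correction is cheap and helps under either reading.

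**What to change.** In Specific Aim 2, Analytic Approach (moderation):

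1. State the outcome as the post-assessment PAPA MDD severity sum score, with the pre-assessment score as a covariate, in line with Aim 1. If the change score is preferred for presentation, keep baseline in the model. Change equals post minus pre, so only the baseline coefficient shifts (by −1), and the interaction coefficient and its SE are identical.
2. Use this same model for the conditional ESL effects and the Johnson-Neyman output.
3. In Power for Moderation, add that the 0.90 was computed for the unadjusted change score. Recomputing it for the adjusted model would need a pre-post correlation that the documents do not give, so a statement is enough.

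The cost is a few sentences in the SAP and about one degree of freedom. Baseline severity is already collected, and the plan itself notes that the macro accepts covariates. Adding the stratification variables as in Aim 1 is optional and is not needed to resolve this point.

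### After a significant ESL × EI interaction, splitting both scores into four cells and testing pairs discards power that the fitted continuous model already has

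*Combined protocol and SAP*

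**What the plan says.** The moderation analysis is in the SAP under Specific Aim 2, Analytic Approach. The main model is continuous: "The independent variable (ESL score) and proposed moderator variable (pre-assessment parental EI) are centered to eliminate any multicollinearity effects". It is probed in two ways. Conditional effects of ESL on MDD severity are reported "at values of EI score equal to selected percentiles (e.g., 10th, 25th, 50th, 75th, and 90th percentiles) of the distribution in the sample". Then "The Johnson-Neyman technique will be used to identify the values of EI score" at which the ESL effect gains or loses significance.

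A third step follows only if EI proves to be a significant moderator: ESL and EI "will be dichotomized so that all subjects fall into 1 of 4 categories", giving low/high ESL crossed with low/high EI. Then: "Post-hoc pair-wise comparisons of treatment outcome in these 4 groups will be conducted".

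The SAP gives no cut point for either score, no adjustment for EI within cells, and no power for the cell comparisons. Nor does it say which result takes precedence if the cells and the continuous model disagree. The Power for Moderation paragraph concerns the continuous interaction only, and there "a simulated dataset of 90 PCIT-ED subjects was created".

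**The concern.** The four-cell step comes after the continuous model has been fitted and probed, and it answers a similar question less well. Three features cause this.

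- **Information loss.** Cutting a continuous score in two treats everyone in a half as alike. Doing so on both axes, then comparing cells of about 15 to 30 people, is much less sensitive than a contrast from the model that uses all the data.
- **Contrasts that isolate nothing.** Four cells give six pairs. Two pairs change ESL within an EI half, two change EI within an ESL half, and two change both at once. No single pair is the difference of differences that defines the interaction being followed up.
- **Residual EI.** Hypothesis 2B expects ESL and EI to be related. If they are, parents with high and low ESL inside the same EI half still differ in EI, so part of a contrast labelled ESL belongs to EI.

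At stake is how a significant moderation result is read. The cell tests could fail to show a pattern that the model has just detected, or sit awkwardly beside the Johnson-Neyman region, and free cut points leave room for analyst choice.

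**Working it through.** **1. The plan's own figure.** From Power for Moderation: coefficient 0.2440, SE 0.0758. t = 0.2440/0.0758 = 3.219. 3.219 − 1.96 = 1.259, and Φ(1.259) = 0.896, which reproduces the stated 0.90. This is the continuous test, and the four-cell step does not touch it.

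**2. Scale of the loss.** For independent normal scores, a double median split multiplies the interaction t by 2/π. 3.219 × 2/π = 2.05; 2.05 − 1.96 = 0.09; Φ(0.09) = 0.54. The plan does not propose an interaction test on the split scores, so this only shows how much information the split removes.

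**3. Power of the within-half ESL comparison at n = 90.** Assumptions not in the documents: median splits; ESL-EI correlation 0.3 to 0.5; in SD units, EI slope 0.5, ESL slope 0.2, interaction 0.2. The split contrast is high versus low ESL in the upper EI half. The model contrast is the ESL slope at the 75th EI percentile, which is the middle of that half. Both are tested at an unadjusted 5%.

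| Setting | Four-cell contrast | Model contrast |
|---|---|---|
| All simulated datasets, n = 90 | 0.46-0.47 | 0.64-0.69 |
| Only those with a significant interaction, n = 90 | 0.57-0.59 | 0.77-0.86 |
| All simulated datasets, n = 180 | 0.77-0.79 | 0.92-0.94 |

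The second row matches how the plan would use the step. The third is shown because the SAP does not state the analysis population outright; 90 is the only figure it gives for this analysis. At n = 90 the upper-half cells hold about 27 and 18 people at correlation 0.3, and 30 and 15 at 0.5.

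**4. A second check on the plan's scale.** The SAP gives "SD=0.22 for ESL, SD=15.6 for EI, SD=4.69 for MDD change score", with group means 2.1 and 2.5 (ESL) and 118 and 99 (EI). An equal mixture has
- ESL SD = √(0.22² + 0.2²) = 0.297
- EI SD = √(15.6² + 9.5²) = 18.3
- implied correlation = −(0.2 × 9.5)/(0.297 × 18.3) = −0.35.

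With correlation −0.35, 0 or +0.35, an assumed EI slope of −0.15 per point and a true interaction sized to t of about 3.22, the within-half ESL comparison has power 0.13-0.30 at 5%. At 0.05/6 it has 0.04-0.11. The planned conditional ESL effects at the 25th and 75th EI percentiles have 0.35-0.42 at 5%.

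**5. Residual EI.** At a correlation of 0.35 in absolute value, the ESL cells within one EI half differ by about 3.7-3.9 EI points. Times 0.15 per point, that is about 0.6 points of MDD change, or 0.6/4.69 = 0.13 SD. At zero correlation there is no leak.

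**6. Does this create false positives?** The scenario has no ESL effect, no interaction and a positive correlation. If the comparison were run in every trial at n = 90, it would be significant in roughly 5-8%. The plan runs it only after a significant interaction, which here occurs in about 5% of trials. The comparison is then both reached and significant in about 1% of trials, and the same holds for the model contrast. An excess appears only with a true interaction and a positive correlation: about 8-14% for the split against 4-6% for the model contrast, among datasets with a significant interaction.

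**The case against.** The best defence is that the proper analysis is already in the plan. The interaction is tested on continuous scores and probed by percentile effects and Johnson-Neyman. The four cells are explicitly post hoc, conditional, and confined to a secondary aim. General Data Analysis Considerations also promises a Holm-type correction for other outcomes, although it does not say whether this covers the six pairs. All of this stands, and it keeps the point small.

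It is also fair that the cut point, correlation and effect sizes are assumed. The sign of the correlation is not settled: Hypothesis 2B implies positive, while the power simulation gives the high-EI group the lower ESL mean, implying negative. So the direction of any residual EI effect is unknown.

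A reader might infer three stronger things, none of which the documents support.

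- **That the split inflates false ESL findings in general.** With no true interaction, the significance condition removes any excess over the model contrast.
- **That the moderation result or its 0.90 power is compromised by this step.** Both rest on the continuous scores.
- **That the cell comparisons would be the headline on which families benefit.** The SAP does not say so and does not rank them above the continuous results.

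The defence does not rescue the tests themselves. Because the better contrasts are already available, the pair-wise tests add less sensitive and partly uninterpretable results.

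**Conclusion.** The point holds as a no-cost improvement to a conditional, post-hoc step. At n = 90, under the stated assumptions, the four-cell ESL comparison among high-EI parents gives up about 0.17 (0.64 − 0.47) to 0.23 (0.69 − 0.46) of power relative to the model contrast. The loss remains when only datasets with a significant interaction are counted, and at n = 180. These sizes would change with other cut points or effects. The finding that two of the six pairs mix ESL and EI needs no assumption. Residual EI within halves is a lesser issue: modest, conditional on a correlation, and of undetermined direction. The Aim 1 analyses and the continuous moderation analysis are not affected.

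**What to change.** In Specific Aim 2, replace the dichotomization and pair-wise tests with contrasts from the fitted continuous model:

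- predicted outcome at the four combinations of the 25th and 75th percentiles of ESL and EI, with confidence intervals;
- the ESL slope at the 25th and 75th percentiles of EI, with confidence intervals.

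This keeps the four-cell display that readers find useful. If observed cells are also wanted, prespecify the cut points and show cell sizes, means and intervals as descriptive only, without tests.

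The cost is a few lines of SAP text. No extra data, subjects or software are needed, since the percentile-based ESL effects are already planned.

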An intent-to-treat analytic approach will be employed. Multiple imputation will be utilized for subjects who discontinue during the study and do not complete the post-treatment assessment. Multiple imputation is desirable because instead of filling in a single value for each missing data point, each missing value is replaced with a set of plausible values, creating multiple imputed datasets. These datasets are then analyzed using standard procedures (that would be appropriate for a single, complete dataset), and results from the multiple data sets are combined into one set of results. The SAS procedures MI and MIANALYZE will be used for creating and analyzing multiple imputed data, resulting in statistically valid results that appropriately reflect the uncertainty due to missing values.

Multiple imputation is a useful method for analysis of datasets with data that are plausibly missing at random (MAR). Missing values rarely occur completely at random (MCAR). Instead, missing values are typically based on other variables, so they are MAR. During the multiple imputation process, the analyst should use all observed variables available in predicting missing values (even variables not used in analysis). If these variables are useful for predicting missing values, the multiple imputation increases power. Furthermore, by using an exhaustive set of predictor variables, the multiple imputation process creates a largely MAR dataset. Thus, multiple imputation can convert missing not at random (MNAR) data to MAR.

Simulation was used to determine sample size needed for analyzing multiple imputed datasets. We assume N=90 completers in each group, so a simulated dataset with N=180 subjects was created. Change in PAPA MDD severity sum scores were generated assuming normally distributed scores with a SD of 4.69 (pooled SD from our pilot RCT) and a mean difference in change scores in the two groups of 2.5. The demographic variables gender, age, race, family income, parental education level, and parental marital status were also included in this dataset. To simulate demographic characteristics, complete demographic profiles from the subjects in our pilot RCT were drawn with replacement 180 times and randomly assigned to the 180 simulated cases. A general linear model of change in PAPA MDD severity sum score by group was conducted for this simulated dataset.

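### The moderation power of 0.90 is not supported by the simulation's own inputs: the recipe as written gives about 0.61 for the printed coefficient, and it has no interaction built in

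*Combined protocol and SAP*

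**What the plan says.** In the Statistical Analysis Plan, Specific Aim 2, Power for Moderation, "a simulated dataset of 90 PCIT-ED subjects was created". It has 45 high-EI and 45 low-EI subjects. One SD is given per variable, "based on our pilot study (SD=0.22 for ESL, SD=15.6 for EI, SD=4.69 for MDD change score". The two groups differ only in their means: "The mean scores for the random normally distributed data varied in the two groups as we expect it to in the proposed study". For the high-EI group "assumed means were 2.1 for ESL, 118 for EI, and -6.5 for MDD change"; for the low-EI group "assumed means were 2.5 for ESL, 99 for EI, and -1 for MDD change". No correlation within the groups and no interaction term is stated. The fitted model returned an ESL by EI interaction "with a coefficient=0.2440 and SE=0.0758", and the SAP converts this single result to power of 0.90.

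The sample-size simulation earlier in the SAP describes the MDD change scores as "normally distributed scores with a SD of 4.69 (pooled SD from our pilot RCT". Power for Mediation uses the same 4.69 as the SD for comparing the two treatment groups.

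**The concern.** One SD per variable, used inside each EI group with different group means, makes the spread across all 90 subjects larger than the SD quoted. For MDD change the plan therefore holds two positions: 4.69 is the SD for a treatment-arm comparison in two places, but the PCIT-ED arm simulated for moderation has a larger SD.

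The spread of ESL and EI largely determines how precisely their product term is estimated. If it is set too wide, the SE is too small and the power too high. A second question is whether the recipe, on any reading of its SDs, produces the SE and the interaction from which 0.90 was read. That figure is the only support the SAP gives for testing Hypothesis 2B with 90 subjects.

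**Working it through.** **Inputs** (all from Power for Moderation unless noted): n = 45 + 45; SDs 0.22 (ESL), 15.6 (EI), 4.69 (MDD change); mean gaps 2.5 − 2.1 = 0.4, 118 − 99 = 19, −1 − (−6.5) = 5.5; coefficient 0.2440, SE 0.0758; critical value 1.96. The origin of 4.69 is in the sample-size simulation text.

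**1. The printed figure.** 0.2440/0.0758 = 3.219; 3.219 − 1.96 = 1.259; Φ(1.259) = 0.896. This agrees with 0.90, so the conversion is correct. The doubt is about what went into it.

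**2. Spread across the 90 subjects.** For two equal groups, overall SD = √(within SD² + (gap/2)²).
- ESL: √(0.22² + 0.20²) = 0.297, 35% above 0.22
- EI: √(15.6² + 9.5²) = 18.3, 17% above 15.6
- MDD change: √(4.69² + 2.75²) = 5.44, 16% above 4.69

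**3. The recipe as written.** In 20,000 datasets with the stated means and SDs, independent normal variables within each group, and least squares on centred ESL, centred EI and their product:
- median SE of the interaction 0.109 (95% range 0.081 to 0.147)
- SE of 0.0758 or less in 0.8% of runs
- mean interaction about 0; rejection rate 4.7% at two-sided 0.05
- |t| of 3.219 or more in 0.16% of runs

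Holding the coefficient at 0.2440: 0.244/0.109 − 1.96 = 0.28, and Φ(0.28) = 0.61.

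**4. Sensitivity to the meaning of the SDs.** If a pilot SD is an overall SD and the plan's gap is kept, the within-group SD is √(SD² − (gap/2)²): ESL 0.092, EI 12.4, change 3.80.

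| SDs treated as overall | Within-group SDs (ESL / EI / change) | Median SE | Φ(0.244/SE − 1.96) |
|---|---|---|---|
| none (as written) | 0.22 / 15.6 / 4.69 | 0.109 | 0.61 |
| change only | 0.22 / 15.6 / 3.80 | 0.092 | 0.76 |
| change and EI | 0.22 / 12.4 / 3.80 | 0.109 | 0.61 |
| ESL and EI | 0.092 / 12.4 / 4.69 | 0.183 | 0.27 |
| all three | 0.092 / 12.4 / 3.80 | 0.150 | 0.37 |

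Dropping the two-group device and drawing trivariate normal data with overall SDs 0.22, 15.6 and 4.69 gives SE 0.152 and power 0.36 with no correlations. With modest assumed correlations (ESL–EI 0.3, ESL–change −0.25, EI–change −0.35) it gives SE 0.135 and power 0.44.

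**5. Detectable interaction at 0.90 power.** (1.96 + 1.28) × SE = 3.24 × SE: 3.24 × 0.109 = 0.35 for the recipe as written; 3.24 × 0.150 = 0.49 if all three SDs are overall.

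**The case against.** A reader might infer that over-dispersed ESL and EI are what produced 0.90. The documents do not support that. With the SDs exactly as printed, the expected SE is already 0.109, so the fall from 0.90 to 0.61 has nothing to do with what the SDs mean. The printed SE is an unusual result even for the plan's own recipe.

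A reader might also infer that all three pilot SDs are shown to be overall SDs. Only 4.69 has a stated origin. Correcting it alone helps the plan (0.76), and correcting change and EI together leaves 0.61. With the plan's gaps kept, the further loss of 24 points (0.61 to 0.37) therefore depends on reading 0.22 as an overall ESL SD, which no section says. The indirect evidence is mixed:
- With EI means 118 and 99 and SD 15.6, Φ(−9.5/15.6) = 27% of the high-EI group falls below the midpoint of 108.5. That is odd for a high/low split, but the SAP gives no cut-point and analyses EI as continuous, so the groups may simply be overlapping generating groups.
- The widest gap between two halves of a normal score with SD 0.22 is 2 × √(2/π) × 0.22 = 0.35, below the assumed 0.4. This may mean that the gap is too wide or that 0.22 is not an overall SD.

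Finally, every power in the table takes 0.244 as the true effect. With independence within groups the recipe has no interaction, and 0.244 is then a chance estimate from one dataset. The tabulated powers show how far the SE matters; none of them can be put in place of 0.90.

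All of this stands as a limit on the claim. It does not rescue 0.90, because no reading of the SDs examined here gives more than 0.76 for that coefficient.

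**Conclusion.** The stated power of 0.90 does not follow from the inputs given for it. Two parts need no assumption about the ESL and EI SDs. First, the simulated arm has an MDD change SD of 5.44, against the 4.69 used elsewhere. Second, the recipe as written gives an SE near 0.109 and power of about 0.61 for a coefficient of 0.244, while building in no ESL by EI interaction. The second part assumes independence within groups, since no within-group correlation is stated.

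Conditional on 0.22 and 15.6 also being overall pilot SDs, power for the same coefficient is about 0.37 with the plan's mean gaps, or 0.36 to 0.44 for trivariate normal data with no to modest correlations. This concerns one power statement for a secondary aim. It has no bearing on the validity of the planned moderation test.

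**What to change.** In Power for Moderation:
1. State for each pilot SD whether it is overall or within EI group.
2. Generate ESL, EI and MDD change so that their SDs across the PCIT-ED arm match the pilot, and state the within-arm correlations and the ESL by EI interaction being assumed.
3. Analyse many simulated datasets of 90 and report the proportion in which the interaction is significant.
4. Replace 0.90 with that proportion, or with the interaction detectable at 0.90 power (about 0.35 for the recipe as written, about 0.49 if all three SDs are overall).

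The cost is a short simulation, one revised paragraph, and a probably less favourable power statement for Hypothesis 2B. No patients or procedures are added; enrolment and the Aim 1 analyses do not change.
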